**Delta 24h UOsm (Baseline vs. 3 months, 6 months, 9 months and 12 months):**

- Control Group: Those with a decrease in delta 24h UOsm not greater than 25% from baseline.
- Intervention group: Those with a decrease in delta 24h UOsm of at least 50% from baseline.

**OR Delta 24h UVol (Baseline vs. 3 months, 6 months, 9 months and 12 months):**

- Control Group: Those with an increase in delta 24h UVol not greater than 500 mL from baseline.
- Intervention group: Those with an increase in delta 24h UVol of at least 1000 mL from baseline.

Furthermore, all individuals attending a clinic study visit (V3, V6 or V8) in a non-fasted state will be excluded from the per protocol analyses. Some other protocol deviations let to exclude patients are detailed in Section 5.1.2

Missing data

Missing data on outcomes (i.e. change of fasting glucose and the secondary cardiometabolic measures) will not be imputed, so subjects with missing data on outcome parameters will not be included in analysis of the respective outcome. For each of the outcomes, the maximum number of subjects will be included (e.g. if there are n=544 evaluable subjects for fasting glucose change, all of these will be included even if there are less evaluable subjects for any other cardiometabolic outcome parameter).

Given the randomized nature of the study, we will not perform any adjustments (which in turn can be affected by missing data on the covariates adjusted for) with three exceptions: (1) As detailed in “statistics” we will include adjustment for the baseline value of the outcome parameter in question (e.g. the change of glucose outcome will be adjusted for the baseline value of glucose). The motif of this adjustment is to minimize bias related to regression towards the mean. (2) As the randomization is stratified by sex, this covariate will be included in all outcome analyses. (3) If clinically significant/meaningful treatment group differences appear in baseline values of age, BMI or diabetes status in any outcome analysis, we will add a sensitivity outcome analysis in which we adjust for such baseline differences. Any missing values for these covariates will be imputed to obtain the same number of evaluable subjects in non-adjusted and adjusted analyses. The technique we propose is Multiple Imputation by Chained Equations (MICE) with subsequent application of Rubin’s rule to combine results from different imputations. We will base the analyses on 20-30 imputed data sets. For this analysis we will use SAS PROC MI in combination with PROC MIXED/PROC GLM and PROC MIANALYZE.

## 5 Planned analyses

### 5.1 Status of subjects, protocol deviations and population definition

#### 5.1.1 Status of subjects

The number of subjects will be provided for the following groups:

- Subjects who attended V2 and fulfilled low water intake criteria (based on urine volume, urine osmolality and plasma copeptin) were randomized. We will thus detail numbers of subjects randomized (total and in intervention and control groups, respectively).
- Of those who were randomized at V2, not all appeared to visit 3, where a baseline clinical examination was performed and therapy (intervention or control) commenced. Thus, number

(total and per intervention/control group) who commenced therapy will be detailed next, including the number and percentage who dropped out between randomization (V2) and baseline exam/start of study (V3) in total and per study treatment group.

- We will detail the numbers who were present at V3, V6 and V8 (totally and per study treatment group).
- We will detail the numbers who completed the study for the intention to treat analysis (i.e. subjects randomized who underwent baseline exam/commenced the study treatment and had at least one additional measurement of fasting glucose (at V6 or V8), in total and per study treatment group).
- Of randomized subjects who attended baseline exam and commenced study treatment (i.e. attended V3), we will detail the number (total and per study treatment group) who dropped out after V3 without at least one additional study fasting glucose measurement (i.e. not completed subjects).

The current numbers at early visits (V2-3) and preliminary numbers on late visits (V6) are given in the section above.

### 5.1.2 Protocol deviations

So far identified protocol deviations are:

Main protocol deviation:

The main protocol deviation is lack of compliance to active or control therapy, for which assessment of 24-hour urine is the best indication. We will address this in per protocol analyses, please see details in section above (part 4.1).

Other protocol deviations:

\*Attendance at clinic study visit outside the predefined time windows. The time between visits summary statistics will be shown but will not result in any per protocol analyses.

\* Attendance at clinic study visit V3, V6 or V8 in a non-fasted state. These participants will be excluded from the per protocol analyses.

Thus, we will detail the numbers of subjects (total and per study treatment group) who had any protocol deviation for these respective reasons, or for other reasons not yet encountered.

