### 3.3 Sample size

The primary outcome parameter is the difference between active (=extra water) and control treatment in the change of fasting plasma glucose between baseline and 12 months. We use prior effect estimates from the largest RCT for diabetes prevention study in Europe, i.e. the Finnish Diabetes Prevention Study (FDPS) (New Engl J Med 2001;344:1343-50), which compared individual life style counselling (active treatment) with general oral and written life-style advice (control treatment) in relation to risk of new onset type 2 diabetes and change of plasma glucose concentration and found a 58% decreased relative risk of diabetes. After 12 months, the fasting glucose in the active treatment group was reduced by  $4 \pm 12$  mg/dL vs a  $1 \pm 12$  mg/dL increase in the control group with the mean difference of 5 mg/dL of the 12-month change of fasting glucose being highly significant ( $P < 0.001$ ).

To obtain sufficient statistical power to detect a clinically significant effect size, we base the power calculation on an effect of water vs control that is at least 50% of what is considered an epoch changing effect of lifestyle i.e., the difference observed in the FDPS, while assuming the standard deviation for the change ( $s = 0.67$  mmol/L) as observed in FDPS. To be able to detect  $\geq 50\%$  of that effect (a difference of 2.5 mg/dL = 0.14 mmol/L between treatments in 12-month change) we need 319 evaluable subjects in both the active and control treatment group at a power of 80% and a 2-tailed significance level of =0.05, a total of 638 evaluable subjects. As the glucose measurement in the study used a more recent and exact method, the standard deviation of the change of glucose was recalculated by the DSMB in October 2022 from the first completed 357 study participants ( $s = 0.58$  mmol/L). With this smaller standard deviation, the power (with all other assumptions unchanged) was 270 evaluable subjects per group, i.e.  $n=540$  evaluable subjects in total. When also taking into account a dysbalance (with slightly higher drop-out rate in subjects in the intervention group), a total of 544 evaluable subjects were estimated to be needed for 80% power.

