#### Intention to treat

The “Intention-to-Treat” population: all randomized study subjects with at least two during study fasting plasma glucose measurements will be analyzed in intention to treat analysis (i.e. regardless of any protocol deviations). This analysis set includes the evaluation of primary and secondary outcomes as well as adverse events (AE) and serious adverse events (SAE) between intervention and control group.

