## **7 Changes in the SAP with respect to the protocol**

SAP Section	Change	Rationale
3.3	Sample size	The reason for the recalculation is that the instruments used are more accurate in the measurements than the instruments used in the Finnish Diabetes Prevention Study (FDPS). The pooled standard deviation of delta fasting plasma glucose (mmol/L) at month 12 is 0.58.

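### The SAP does not say what happens to glucose from a non-fasted visit in the ITT analysis; on the natural reading it enters the primary fasting-glucose model

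*SAP*

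**What the plan says.** SAP 5.1.2 lists deviations identified so far. One is "Attendance at clinic study visit V3, V6 or V8 in a non-fasted state. These participants will be excluded from the per protocol analyses". SAP 4.1, at the end of the per-protocol rules, repeats it: "all individuals attending a clinic study visit (V3, V6 or V8) in a non-fasted state will be excluded from the per protocol analyses". Neither section states any other consequence.

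The ITT paragraph of SAP 4.1 takes all randomised participants who have at least two fasting plasma glucose values during the study. They "will be analyzed in intention to treat analysis (i.e. regardless of any protocol deviations"). SAP 5.1.3 adds that one of the two values is at V3 and the other at V6 or V8. The missing-data part of SAP 4.1 says outcomes are not imputed and that each outcome uses as many participants as possible.

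The primary model (SAP 5.6.2) takes the change in fasting plasma glucose at 6 and 12 months as the dependent variable, with baseline fasting glucose as a covariate. No section sets a non-fasted value to missing or plans a sensitivity analysis for fasting state. The outlier analysis in SAP 6.5 is optional and not linked to it.

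**The concern.** Keeping a participant in the analysis despite poor adherence is what intention to treat requires. Keeping a sample that does not measure the endpoint is a separate matter, and intention to treat does not require it. A non-fasted V6 or V8 puts a non-fasting value into the outcome. A non-fasted V3 puts one into the baseline covariate and into both change scores. Fasting insulin and triglycerides are affected in the same way. So are the fasting-glucose criterion for new-onset diabetes (SAP 5.7.2) and the impaired-fasting-glucose subgroup (SAP 6.6).

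Two things are at stake. Such values add variance to a comparison sized to detect 0.14 mmol/L. They also bias it if one arm attends non-fasted more often, and participants in this trial necessarily know their arm. In addition, if the rule is settled only when the data are in hand, membership of the primary analysis set is settled then too.

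**Working it through.** **Two readings of the text.**
- *Natural reading.* Non-fasted attendance is a protocol deviation, ITT ignores deviations, and the maximum number of participants is used. The value stays in.
- *Strict reading.* ITT membership and the endpoint are both defined by fasting measurements, so a non-fasted sample is not one. It is missing, and a participant with a non-fasted V3 is not in the ITT set.

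The SAP does not choose between them, and they give different ITT sets.

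**Inputs from SAP 3.3, 5.1.3 and 7.** The target is "a difference of 2.5 mg/dL = 0.14 mmol/L between treatments in 12-month change". The test is two-sided at 0.05 with 80% power. "The pooled standard deviation of delta fasting plasma glucose (mmol/L) at month 12 is 0.58". The expected evaluable sample is 544, split 46:54.

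**Reproducing the plan.**
- Per group: n = 2 × [(1.960 + 0.842) × 0.58 / 0.14]² = 2 × 134.7 = 269.4, so 270, as stated.
- At 46:54: N = 134.7 / (0.46 × 0.54) = 542.3, so 543 (the SAP has 544).
- Power at 544: SE = 0.58 × √(1/250.2 + 1/293.8) = 0.0499, and Φ(0.14/0.0499 − 1.96) = 80.1%.

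**Noise, on raw change scores.** The documents give neither the share of non-fasted visits nor the glucose rise, so everything in this step is assumed. Let a share p of V3 and of V8 values be non-fasted, independently and equally in both arms, with a rise of mean μ and SD τ (mmol/L). Take 0.58 as free of such values. Then SD² = 0.58² + 2[pτ² + p(1−p)μ²].

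Example, p = 1%, μ = τ = 1: 0.3364 + 2(0.0100 + 0.0099) = 0.3762, so SD 0.613 and power 75.6%. Setting the values to missing leaves 544 × 0.99² = 533 complete V3–V8 pairs at SD 0.58, with power 79.3%.

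| p | μ, τ | SD, values kept | Power, kept | Power, set to missing |
|---|---|---|---|---|
| 0.5% | 0.5, 0.5 | 0.584 | 79.5% | 79.7% |
| 1% | 0.5, 0.5 | 0.589 | 79.0% | 79.3% |
| 1% | 1, 1 | 0.613 | 75.6% | 79.3% |
| 2% | 1, 1 | 0.645 | 71.4% | 78.5% |
| 5% | 0.5, 0.5 | 0.621 | 74.6% | 76.0% |
| 5% | 1, 1 | 0.729 | 60.7% | 76.0% |

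**With the planned baseline adjustment.** Assume equal variance at V3 and V8 and a baseline SD b of 0.6 or 1.0 (not in the documents). The covariance is b² − 0.58²/2, each visit's variance is V = b² + pτ² + p(1−p)μ², and the residual variance is V − cov²/V. For b = 0.6, p = 1%, μ = τ = 1: cov = 0.1918, V = 0.3799, residual variance = 0.3799 − 0.0968 = 0.2831, SD 0.532, power 86.4%. Without non-fasted values it is about 89%, a loss of 2.9 points. For b = 1.0, power is 79.5% against about 83%, a loss of 3.9 points. On raw change scores the loss was 80.1 − 75.6 = 4.5 points.

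**If 0.58 already includes non-fasted values.** Planned power stays at 80.1%. For p = 1%, μ = τ = 1 the SD without them is √(0.3364 − 0.0398) = 0.545, and removing them gives 84.1%. For μ = τ = 0.5 it gives 80.5%.

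**Bias.** The shift at V8 is the arm difference in p times the rise: 0.01 × 1 = 0.01 mmol/L (7% of 0.14) and 0.01 × 2 = 0.02 mmol/L (14%).

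**The case against.** - **The SAP never says that non-fasted glucose is analysed as fasting glucose.** This is correct. A reader might infer from SAP 5.1.2 that such values certainly enter the primary analysis. The wording of the ITT definition, and of SAP 5.1.1 and 5.1.3, leaves the strict reading open. What stands is that the text does not decide, while the rule on deviations and the rule on maximum numbers both point towards keeping the values.
- **A reader might infer that the trial is underpowered.** The documents do not support this. The SD comes from the trial's own data: "the standard deviation of the change of glucose was recalculated by the DSMB in October 2022 from the first completed 357 study participants". If non-fasted values are kept, some may already be inside 0.58, and adding them again counts them twice. Baseline adjustment also absorbs part of the error at V3, and the rate and rise are assumed.
- **Removing values is not free.** With p = 1% and a constant rise of 0.5, SD² = 0.3364 + 2 × 0.01 × 0.99 × 0.25 = 0.3414. Power is then about 79.5% with the values kept and 79.3% with them missing. If rises are that small and uniform, keeping them costs nothing in power.
- **Safeguards exist.** Deviation counts will be reported by arm, and the primary model is rerun per protocol. The counts help. The per-protocol set cannot isolate fasting state, because it also excludes on urine measures.
- **Excluding the whole person from per protocol could be called a fault.** It is a preference. Removing deviators is how the SAP defines that secondary set.

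**Conclusion.** The point holds as a cheap improvement. The only stated handling of a non-fasted V3, V6 or V8 is exclusion from per protocol. On the natural reading, non-fasting values enter the primary fasting-glucose analysis and the other fasting analytes. The alternative reading is defensible and gives a different ITT set, so the SAP needs a rule under either.

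The direction is clear: more noise, and bias if non-fasting differs by arm. The bias is small, 0.01 to 0.02 mmol/L per one-point arm difference for an assumed rise of 1 to 2 mmol/L. The size of the power effect cannot be taken from the documents. On raw change scores, with 0.58 taken as clean, it runs from negligible with rare, small rises to several points at 1 to 2% of visits with a mean rise of 1 mmol/L. The 5% row with that rise is the far corner of an assumed range, and nothing in the documents points to it. If 0.58 already contains these values, there is no shortfall against plan. Removing them would then generally raise power above 80%.

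**What to change.** 1. In the primary ITT analysis, set glucose and the other fasting analytes to missing at any visit recorded as non-fasted, and keep the participant's other visits. The mixed model already handles missing follow-up under missing at random.
2. State the rule for V3 explicitly. A participant with a non-fasted V3 has no valid fasting baseline and is not evaluable for change in that analyte. The SAP places randomisation before V3, so these are losses after randomisation and should be reported by arm.
3. Report non-fasted visits by arm and visit.
4. Run the version with all values as a sensitivity analysis. It retains the participants lost under step 2.
5. Say in SAP 3.3 whether the 0.58 estimate included non-fasted values.

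The cost is a few sentences in the SAP. A few values become missing, and participants with a non-fasted V3 leave the primary analysis. In the table above, setting values to missing brings power from 80.1% to between 79.7% and 76.0%, depending on the share assumed. That counts only complete V3–V8 pairs, although a participant without a valid V8 still contributes V6 to the mixed model.

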### 5.1.3 Populations

We expect a final study sample for intention to treat analysis of at least n=544 evaluable study subjects who have completed the protocol (i.e. with at least 2 fasting glucose measurements, meaning at V3 and at either V6 or V8 or at both V6 and V8). We expect a dysbalance in the final study sample (46% intervention vs 54% control therapy) due to dysbalance in the drop-out rate between intervention and control groups.

## 5.2 Demography

Variable name and unit	Variable source 	Type 	Unit	Set 
Sex	R	N	male/female	ITT, PP

Age	R	C	years	ITT, PP
1.	(R)aw or (D)erived data			
2.	(C)ontinuous or (O)rdinal or (N)ominal			
3.	Intention to treat (ITT) or Per Protocol (PP)			

### 5.3 Baseline characteristics

Variable name and unit	Variable source 	Type 	Set 
SURVEY			
Diabetes mellitus	R	N	ITT, PP
Hypertension	R	N	ITT, PP
Cardiovascular disease	R	N	ITT, PP
Cancer	R	N	ITT, PP
CLINICAL			
Height (cm)	R	C	ITT, PP
Weight (Kg)	R	C	ITT, PP
BMI (Kg/m  )	D	C	ITT, PP
Waist circumference (cm)	R	C	ITT, PP
Systolic blood pressure (mm Hg)	R	C	ITT, PP
Diastolic blood pressure (mm Hg)	R	C	ITT, PP
Body fat%	R	C	ITT, PP
BLOOD			
Fasting glucose (mmol/L)	R	C	ITT, PP
Fasting and 2h glucose (during OGTT) (mmol/L)	R	C	ITT, PP
Fasting and 2h insulin (during OGTT) (mIE/L)	R	C	ITT, PP
Fasting HbA1c (mmol/mol)	R	C	ITT, PP
Fasting cortisol (nmol/L)	R	C	ITT, PP
Fasting ACTH (pmol/L)	R	C	ITT, PP
Fasting copeptin (pmol/L)	R	C	ITT, PP
Fasting Apo A1 (g/L)	R	C	ITT, PP
Fasting ApoB (g/L)	R	C	ITT, PP
Fasting Triglycerides (mmol/L)	R	C	ITT, PP
Fasting LDL (mmol/L)	R	C	ITT, PP
Fasting HDL (mmol/L)	R	C	ITT, PP
C-reactive protein (mg/L)	R	C	ITT, PP
Creatinine (μmol/L)	R	C	ITT, PP
eGFR (mL/min/1,73 m  )	D	C	ITT, PP
Sodium (mmol/L)	R	C	ITT, PP
Potassium (mmol/L)	R	C	ITT, PP
Urea (mmol/L)	R	C	ITT, PP
Osmolality (mOsm/kg)	R	C	ITT, PP
Erythrocyte Volume Fraction (%)	R	C	ITT, PP
URINE			
Volume (ml)	R	C	ITT, PP
Osmolality (mosm/kg H 2 O)	R	C	ITT, PP
Creatinine (mmol/24h)	R	C	ITT, PP

Sodium (mmol/24h)	R	C	ITT, PP
Potassium (mmol/24h)	R	C	ITT, PP
Urea (mmol/24h)	R	C	ITT, PP
Albumin/creatinine ratio (g/mol)	R	C	ITT, PP

1. (R)aw or (D)erived data
2. (C)ontinuous or (O)rdinal or (N)oinal
3. Intention to treat (ITT) or Per Protocol (PP)

#### 5.4 Study conducts parameters

Variable name	Variable source 	Type 	Unit	Set 
Compliance parameters (markers of urine concentration)				
V6 vs V3 urine osmolality difference (paired test)	D	C	mosm/kg	ITT, PP
V8 vs V3 urine osmolality difference (paired test)	D	C	mosm/kg	ITT, PP
V6 vs V3 urine volume difference (paired test)	D	C	mosm/kg	ITT, PP
V8 vs V3 urine volume difference (paired test)	D	C	mosm/kg	ITT, PP

1. (R)aw or (D)erived data
2. (C)ontinuous or (O)rdinal or (N)oinal
3. Intention to treat (ITT) or Per Protocol (PP)

Study conduct parameter derivations:

Study duration (days): time between the last visit (V8) and randomization visit  
 $= (\text{Date of V8} - \text{Date of V3}) + 1$  will be detailed.

Compliance to study urine volume (see paragraph 5.4 above): This will be used to assess compliance in per protocol analysis.

Time between study visits (days): time between each study visit planned in the study.  
 $= (\text{Date of Vy} - \text{Date of Vx}) + 1$  with  $y > x$ . It will be calculated between V3 – V6, V6 – V8 and V3 – V8 and presented.

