Fasting cortisol (nmol/L)			+			+		+
Fasting ACTH (pmol/L)			+			+		+
Fasting copeptin (pmol/L)			+			+		+
Fasting Lipids/lipoproteins ^e (mmol/L)/(g/L)			+			+		+
C-reactive protein (mg/L)			+			+		+
Creatinine (µmol/L)	+		+	+	+	+	+	+
eGFR (mL/min/1,73 m ²)	+		+			+		+
Sodium (mmol/L)	+		+	+	+	+	+	+
Potassium (mmol/L)			+	+	+	+	+	+
Urea (mmol/L)			+	+	+	+	+	+
Osmolality (mOsm/kg)			+	+	+	+	+	+
Erythrocyte Volume Fraction (%)			+					+
HbA1c (mmol/mol)			+					+
Plasma samples for long term storage			+			+		+
Whole blood for DNA isolation			+					
URINE								
24-hour urine sample		+		+	+	+	+	+
Urine volume (ml)		+		+	+	+	+	+
Creatinine (mmol/24h)		+		+	+	+	+	+
Sodium (mmol/24h)		+		+	+	+	+	+
Potassium (mmol/24h)		+		+	+	+	+	+
Urea (mmol/24h)		+		+	+	+	+	+
Osmolality (mOsm/kg)		+		+	+	+	+	+
Albumin/creatinine ratio (g/mol)		+				+		+
Cortisol (nmol/24h)		+				+		+

Urine for long term storage		+				+		+
FAECES								
Sample for microbiome seq			+					+
Bristol stool score			+					+
Check for adverse events				+	+	+	+	+
^a Pre-randomization. ^b Time after randomization. ^c Clinic visits 8 time points: visit 1, visit 2, baseline, 3 weeks & 3, 6, 9 and 12 months after baseline. ^d In addition to coaching during telephone contacts and by a Bluetooth water bottle. ^e triglycerides, LDL, HDL, ApoA1, ApoB.								

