Blood samples for long-term storage (biobank) are centrifuged immediately after blood draw. Then they are stored in the fridge for approximately 1-3 hours before being aliquoted and transferred (transported on ice) to the -80 degree freezer in another close-by building, approximately a 5 minute-walk from the clinical site. These samples are also transported by site staff. Assays on the biobank samples will be performed after all study subjects have completed the protocol in the same batch of reagents (includes analysis of copeptin, see above).

Blood sample measures: All routine laboratory analyses will be performed using certified methods at the University Hospital's central clinical lab, including measurement of plasma glucose (COBAS, Roche Diagnostics, Rotkreuz, Switzerland), serum insulin, serum glucagon, plasma cortisol, plasma ACTH, lipids/lipoproteins, c-reactive protein, serum creatinine, serum sodium, serum urea, serum osmolality, serum haematocrit and glycated hemoglobin (HbA1c).

Plasma copeptin will be measured in our lab (located at [name], Skåne University Hospital, Malmö) in 50 µl from fasting plasma samples stored at -80°C using a commercially available chemiluminescence sandwich immunoassay copeptin ProAVP kit with coated tubes (B.R.A.H.M.S AG, Hennigsdorf, Germany).

Procedure for OGTT: After an over-night fast (no meals or drinks after 10PM the evening before), subjects will ingest 75 g of glucose over a maximum period of 3 minutes, starting sometime between 730 and 9 AM, followed by blood sampling for glucose measurement at 30, 60 and 120 min.

Handling of urine samples: 24-hour urine samples will be collected at baseline and again at 3-weeks, and 3, 6, 9, 12 months after randomization. 24-hour urine collections follow procedures developed at the Department of Endocrinology, Skåne University Hospital, and consists of a comprehensible written instruction aimed at ensuring accurate and complete collection of urine. The procedure has been used by us in many large research studies (see for example applicant references 5 and 10). The participants start the 24-hour urine collection one day before a planned visit, and bring their container on the day of visit. For example, if their visit is on a Wednesday they start collecting urine on a Tuesday. The first urine on Tuesday morning is not collected. The

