### 3.2 Study design

The study is a parallel-group RCT with two arms during 12 months. Subjects with the age of 20-75 years will be randomized to the water-intervention (1.5 L total on the top of habitual intake) and control group (1:1). The randomization will be stratified by gender to pursue equal distribution of intervention and control group for both male and female subjects. Both groups will receive general lifestyle advice (general oral and written advice on diet and physical activity). Reusable Bluetooth water bottles, which are volume sensitive and can be linked to an Android or iPhone application for individual monitoring purposes will be provided to subjects in the active treatment arm.

Study subjects will be recruited from 4 ongoing population studies in the Scania region encompassing altogether approximately 20 000 individuals within the current age span. Copeptin will be measured in -80 degrees frozen plasma samples from these 4 population studies. Individuals having a copeptin concentration of  $>6.1$  pmol/L (women) or  $>10.7$  pmol/L (men) will be invited to participate in the screening and inclusion process of this study. If fewer than expected will be recruited from these 4 studies, letters of invitation will be sent to inhabitants of the City of Malmö with surroundings, and inhabitants will also be invited through advertisements in local newspapers and social media. The same copeptin cut-off values will be used for inclusion to the study regardless of which invitation process that was used to include the participant.

All included individuals are low drinkers with high urine osmolality ( $U_{osm} \geq 600$ ) and low urine volume ( $U_{vol} \leq 1,5L$ ) as specified in the following figure.

Clinic visits are performed at 8 time points: visit 1, visit 2, baseline (visit 3, V3), 3 weeks and 3, 6 (visit 6, V6), 9 and 12 (visit 8, V8) months at which cardiometabolic risk factors and hydration parameters are measured (not all parameters at all time points). The study design is visualized in the Figure below.

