### 3.4 Changes in the conduct of the study compared to the protocol

The key compliance/adherence measure during the study is 24-hour urine measurement of volume and osmolality. After the start of study treatment at V3, 24-hour urine is collected at V4 (3 weeks), V5 (3 months), V6 (6 months), V7 (9 months) and V8 (12 months). Apart from the main “intention to treat” analysis, we will perform “per protocol” analysis in which we exclude subjects with major protocol deviations (i.e. whose values of 24-hour urine displays major deviation from expected, given treatment assignment, with those limits defined below (see protocol deviations)).

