## 4 Analysis sets

### 4.1 Analysis sets

#### -Included subjects

Urine collection over 24 hours is collected from participants in previous population studies and from subjects living within the greater Malmö area who respond to advertising. The analysis set is the number of subjects who fulfill all inclusion criteria (including urine volume, osmolality and plasma copeptin) and are randomized to treatment allocation after V2.

At the following “baseline visit” (V3), baseline fasting metabolic measurements are done and after the baseline visit (V3), the actual active and control treatment commence. This design is the only one practically possible as study subjects need to perform the baseline measurements in the morning in the fasted state. However, of the subjects included and randomized to treatment allocation at V2 some are expected to not come to the V3 fasting baseline examination and thus never commence active or control treatment. Furthermore, of all subjects starting intervention after V3, we will probably observe a dropout during the study.

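### SAP 5.4 judges compliance by paired urine changes from V3, but the comparator is most likely the selected V2 inclusion sample, so regression to the mean would read as higher water intake

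*SAP*

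**What the plan says.** SAP 5.4 lists four compliance parameters: urine osmolality and urine volume, each at V6 and at V8, compared with V3. The entries read "V6 vs V3 urine osmolality difference (paired test" and "V6 vs V3 urine volume difference (paired test". Of urine-volume compliance, the same section adds: "This will be used to assess compliance in per protocol analysis". SAP 5.7.1, which defines the variables that go into the between-arm mixed model, lists only the albumin/creatinine ratio under urine.

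On timing, the Protocol's Table 1 row "24-hour urine sample" is marked at the inclusion visit (visit 2), at 3 weeks, and at 3, 6, 9 and 12 months. The baseline (week 0) cell is empty, as it is for urine volume and osmolality. The Protocol text under Handling of urine samples says "24-hour urine samples will be collected at baseline and again at 3-weeks, and 3, 6, 9, 12 months after randomization". SAP 3.4 states "After the start of study treatment at V3, 24-hour urine is collected at V4 (3 weeks" and continues the list to V8. For V3, SAP 4.1 mentions that "baseline fasting metabolic measurements are done and after the baseline visit (V3" treatment starts; it names no urine collection.

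On selection, SAP 3.2 states "All included individuals are low drinkers with high urine osmolality" and low urine volume. The Protocol requires osmolality above 600 mosm/kg and excludes volumes of 1.5 L or more.

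**The concern.** A paired test against a value that had to be extreme for the subject to be enrolled mixes two things: a real change in drinking, and the drift back toward the subject's usual level that any repeat sample would show. If the V3 value is really the V2 inclusion sample, the control arm will appear to have raised its water intake, and part of the apparent response in the intervention arm will be drift.

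This matters because SAP 3.4 calls 24-hour urine the key adherence measure. A null glucose result can be interpreted only if separation in water intake is credible, and control-arm contamination is one of the two adherence failures that SAP 4.1 describes. The SAP already adjusts the outcome analyses for baseline in order to limit regression to the mean, but does not do so for urine compliance. The per-protocol cut-offs are also measured from baseline. Drift pushes controls toward failing theirs and intervention subjects toward meeting theirs.

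**Working it through.** The plan gives no figure for this effect, so there is none to reproduce.

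**Step 1: which sample is the comparator.** Table 1 marks six collections: visit 2 plus five follow-ups. The Protocol text also counts six: baseline plus 3 weeks and 3, 6, 9 and 12 months. The counts match if baseline in the text means the visit 2 sample. SAP 3.4 (V4 to V8) and SAP 4.1 (fasting metabolic measurements at V3) agree with that reading. Against it stand the V3 label in SAP 5.4, the definition of V3 as the baseline visit, and the listing of urine volume and osmolality as baseline characteristics in SAP 5.3. V2 is the more likely source, but this is not settled.

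**Step 2: direction.** For a normal variable with mean μ, SD σ and repeat correlation ρ, selected on a first value above c, the expected fall with no behaviour change is (1 − ρ) × σ × φ(z)/(1 − Φ(z)), where z = (c − μ)/σ. It is positive whenever ρ < 1. With c = 600:
- μ = 725, σ = 180, ρ = 0.7: z = −0.694, φ/(1 − Φ) = 0.314/0.756 = 0.415, fall = 0.3 × 180 × 0.415 = 22 mosm/kg.
- μ = 550, σ = 210, ρ = 0.5: z = 0.238, φ/(1 − Φ) = 0.388/0.406 = 0.955, fall = 0.5 × 210 × 0.955 = 100 mosm/kg.

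The mean, SD and correlation are assumptions; the documents give none of them.

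**Step 3: size, with selection on volume as well.** Simulation with no change in intake, selecting on osmolality > 600 and volume < 1.5 L. Controls: 544 × 0.54 = 294 (SAP 5.1.3).
- Assumed mean 550–725, SD 180–210, correlation 0.5–0.7: fall of about 26–125 mosm/kg, rise of about 85–207 mL, paired t about 3–9. The low ends depend on the assumed volume distribution. A rerun with log-normal values, volume mean 1200 or 1500 mL (SD 400 or 500) and log-scale osmolality–volume correlation −0.7 gave 23–125 mosm/kg and 59–206 mL, with a smallest t of 2.7.
- Wider assumptions (mean 500–700, SD 150–200, correlation 0.4–0.8, volume mean 1500 and SD 500 mL): fall of 19–173 mosm/kg, rise of 72–268 mL, t 3.1–13.3 for osmolality and 5.1–11.2 for volume.
- One scenario in full (mean 600, SD 150, correlation 0.6): selected mean 743, later mean 685, fall 58 (58/743 = 7.8%), SD of the difference 147, t = 58/147 × √294 = 6.8. Volume rises by 155 mL, t = 7.8.

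Every setting is significant at two-sided 0.05. SAP 6.1 states that level for primary and secondary outcomes; it is assumed here for the paired tests.

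**Step 4: per-protocol set.** SAP 4.1 keeps a subject who meets either the osmolality or the volume criterion. A control is therefore removed only by both an osmolality fall above 25% and a volume rise above 500 mL.
- Scenario above, one visit: 17.1% of unchanged controls exceed the osmolality limit, 14.6% the volume limit, 8.0% both.
- Across the mean 550–725 settings: about 9–40% exceed the osmolality limit alone, but about 4–16% fail both.
- Unchanged intervention subjects who reach a 50% fall or a 1000 mL rise: about 1–9% at one visit.
- The SAP does not say how the four listed visits are combined. If changes are averaged over them, joint failure among controls is about 1–11%.

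**Step 5: what removes the artefact.** The urine criteria are applied at V2. SAP 4.1 places randomization after V2, and Table 1 places it at baseline; either way selection comes first, so the expected drift is the same in both arms and cancels in an arm difference. With a separate V3 sample not used for selection, the simulated mean change is within about 1 mosm/kg and 2.5 mL of zero.

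**The case against.** The Protocol says urine is collected at baseline, and the SAP defines V3 as the baseline visit. A reader might infer from Table 1 that V3 urine values do not exist. The documents do not support that; they conflict, and a separate V3 sample would largely dissolve the point. This part of the objection stands, which is why reconciliation comes first.

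SAP 5.4 does not say that the paired tests are run by arm. That is inferred from the word paired and from the absence of any planned between-arm test of these variables. A careful reader could compare the two arm-specific changes and see the common drift, but the plan does not ask for that comparison.

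A reader might also take the share of unchanged controls whose osmolality falls more than 25% (about 9–40%) as the share lost from the per-protocol set, or conclude that intervention adherence is greatly overstated. The either-criterion rule contradicts the first. The distance to the 50% and 1000 mL cut-offs contradicts the second, since mean drift is only 2–22% of the selected osmolality even under the wider assumptions.

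Finally, the magnitudes rest on assumed distributions. Candidates are already selected on copeptin, and the Protocol describes that group as having urine osmolality above 600, so a higher mean and a smaller drift are plausible. The direction is not in doubt; the size is.

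**Conclusion.** The point holds for the compliance summary, conditional on V2 being the source of the V3 urine value, which is the reading that the schedule favours. On that reading an unchanged arm shows a significant fall in osmolality (about 26–125 mosm/kg) and rise in volume (about 85–207 mL), and the paired tests cannot tell this from adherence. The effect on the per-protocol set is real but modest: about 4–16% of unchanged controls wrongly removed and about 1–9% of unchanged intervention subjects wrongly kept, judged at one visit. These figures rest on the assumed means, SDs and correlations; the sign needs only a repeat correlation below 1. The primary intention-to-treat glucose analysis does not use these urine values and is unaffected. Per protocol is a secondary analysis. This is a worthwhile correction to how adherence is reported, not a threat to the main result.

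**What to change.** 1. State in SAP 5.4 and 4.1 which collection supplies the V3 urine value, reconcile this with Table 1 and the Protocol's urine-handling text, and use it consistently.
2. Replace the paired tests as the compliance measure with a between-arm comparison of urine volume and osmolality at the follow-up visits, using the SAP 5.6.2 mixed model adjusted for the pre-treatment urine value and sex. Report the arm difference with its confidence interval at each visit. Keep the paired within-arm changes as description only.
3. If the baseline is V2, add a caveat to the per-protocol results that the cut-offs are measured from a selected sample. Naming V2 as the baseline does not cure this, and the between-arm model corrects the compliance summary only.
4. In the same edit, correct the unit for the volume differences in SAP 5.4, which is printed as mosm/kg.

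The cost is SAP wording and a small amount of extra analysis on data that the plan already collects. Dropout is expected to differ by arm (46% against 54% of the final sample), so the arm difference still relies on the missing-at-random assumption that SAP 5.6.2 makes for glucose.
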